#### 6.6 Proposed types of analyses

Primary efficacy analysis will be intention to treat. Given pragmatic eligibility criteria and up-front one-time treatment, we expect no cross-overs and very few protocol violations. A protected hierarchical analysis plan will be performed. First, non-inferiority will be established if the lower boundary of the 95% confidence interval of the % difference in subjects achieving good outcome (mRS 0-1) in the tenecteplase versus the alteplase arm is greater than -5% (the non-inferiority margin). If non-inferiority is demonstrated, then a test of superiority will be performed as part of secondary analysis. The primary analysis for efficacy will be a stratified Cochran-Mantel-Haenszel (CMH) test where registry (QuICR vs. OPTIMISE) will be used as a stratification variable. If noninferiority is not demonstrated, all subsequent analyses will be considered hypothesis-generating. As sensitivity analysis, logistic regression will be used to provide an adjusted estimate of effect size of the effectiveness of tenecteplase over alteplase. The odds ratio of good 90-day outcome associated with the treatment groups will be estimated using a logistic regression model after adjusting for registry, age, sex, baseline stroke severity and onset-to-needle time. For secondary analyses, frequency tables will be used to summarize binary variables by treatment group. Descriptive statistics will be used to summarize continuous data variables by treatment group. Similar to the primary efficacy variable, binary secondary outcomes will be analyzed using logistic regression analysis. The continuous secondary outcomes will be analyzed using analysis of covariance (ANCOVA) and mixed-effects regression with the registry (QuICR vs. OPTIMISE) variable treated as a randomeffect. If non-inferiority of the primary outcome is demonstrated, a hierarchical multiplicity

adjustment will be used to determine the Type I error for testing the secondary outcomes in order to control the overall familywise type I error rate for the study. Sex will be a unit of analysis. In addition, given previous literature suggesting underutilization of thrombolysis in females, sex-based differences in recruitment, workflow and processes and outcomes will constitute important prespecified subgroup analyses. Details will be provided in the statistical analysis plan that will be developed and reviewed by the trial steering committee.

#### 6.7 Proposed frequency of analyses

Schedule for interim analyses (at every  $1/3^{rd}$  of total patients enrolled; see Table) will be finalized in consultation with the DSMC. The overall principle of interim analyses will be to determine early if tenecteplase causes more mortality OR is significantly inferior than alteplase at interim. The safety stopping rule pertains to a substantial mortality difference favoring alteplase at interim. This rule is met if the observed p-value for mortality comparing randomized groups is below a threshold defined using a power family approach to alpha-spending using  $\varphi=1$ , and if the numeric rate of mortality favors alteplase (e.g., if it is found that tenecteplase is substantially and significantly inferior to alteplase in terms of mortality at interim). For inferiority, the stopping rule is defined in terms of

absolute difference between the tenecteplase and alteplase rates of mRS 0-1; if at interim, the difference  $\Delta$  for mRS 0-1 in the tenecteplase vs. alteplase group is lower (worse) than the indicated value, the trial will be stopped for significant inferiority of tenecteplase as it will be unlikely that the

Evaluable Sample Size	Stopping for Safety Two-Sided Alpha for Mortality	Stopping for Futility Effect size Δ for mRS 0-1
533 (one-third)	0.0167	-10.0%
1067 (two-thirds)	0.0218	-5.0%
1600 (final)	n/a	n/a

effectiveness endpoint can be met. Final analyses will be conducted on completion of the trial.

#### 6.8 Pre-specified subgroup analyses

Subgroup analyses will be performed by registry (QuICR vs. OPTIMISE), type of enrolling hospital (PSCs vs. CSCs), age (continuous and as < 80 years vs. >= 80 years), sex and baseline stroke severity (NIHSS; < 8, 8-15 and > 15). Subgroup analyses will help to determine if there is overwhelming efficacy or futility in any pre-specified subgroup. Subgroup analyses will remain exploratory.

# 7. Trial Management

#### 7.1 Arrangements for day-to-day management of the trial

The study will be managed by the AcT/OPTIMISE Trial Management committee and will be overseen by the QuiCR and OPTIMISE executives. The trial will also have a co-ordinator who will be responsible for the day-to-day management of the trial. The co-ordinator will work closely with the QuICR and OPTIMISE registry personnel to conduct regular trial quality improvement initiatives and to ensure blinded assessment of outcomes. The Clinical Research Unit (CRU) at the University of Calgary and another data management vendor will develop the trial database and Randomization tool

the data management vendor will host the trial database and randomization tool. Subject data will be captured and managed by study sites on a Web-based electronic data capture tool (eCRF) configured by the sponsor and hosted by the electronic data capture vendor. Interpretation of results, manuscript submission for publication, and presentation of results at national and international conferences, will be performed by the Trial Executive.

#### 7.2 Data Confidentiality

The QuICR registry data is entered by registry/Alberta Health Service (AHS) personnel in a secure database at the Clinical Research Unit (CRU) of the University of Calgary. The QuICR registry is operating under a legal agreement (Information Management Agreement – IMA) with AHS, such that the University of Calgary is acting as a manager of identifiable health information for Alberta Health Services. The custodian of the data is the Alberta Health Services. The Alberta Health Service has completed a Privacy Impact Assessment for the QuICR Registry through the Office of the Information and Privacy Commissioner of Alberta that protects confidentiality of data.

OPTIMISE is managed by the Canadian Stroke Consortium. OPTIMISE registry data is entered by site personnel using a simple web-based electronic case report form, held in a REDCap database and stored on a secure server at the Population Health Research Institute at McMaster University. Data entry is handled at each site and quality assurance processes managed at the central data management site. Patient identifiers are not collected centrally. Each patient is assigned a unique OPTIMISE ID #; sites maintain patient logs that link patient identifiers to the unique OPTIMISE ID # in a secure platform.

The electronic data capture vendor will maintain a secure trial database that will link study subject ID with the registry ID. This database will also record SAEs occurring within 24 hours, 90-120 day outcomes and patient contact information. The registry ID in this secure database will be used to link to administrative data sources (e.g. DAD). Details will be provided in the MOP.

The randomization and electronic consent applications will be maintained by the electronic data capture vendor in a secure -managed environment. Both the application and the environment will adhere to industry-standard security practices such as data encryption, regular backups, etc.

The secure final study database will have deidentified data (by Trial ID) from a) the QuICR or the OPTIMISE registry, b) the trial database, c) the electronic consent application and d) the administrative data sources. This data will be stored on password protected and encrypted computers at the University of Calgary, in a statistical program data set.

Paper records will be kept in locked file cabinets or in a secure office. Clinical information will not be released without written permission of the subject, except as necessary for monitoring by ethics committees, regulatory bodies, the sponsor, or the sponsor's designee. All study investigators at the clinical sites must ensure that the confidentiality of personal identity and information of study participants is maintained at all times. Province specific privacy regulations where applicable, must be followed. Only properly authorized persons will have access to any records. Personal medical information is always treated as confidential.

#### 7.3 Ethics

Where approved by the local ethics review board, to reduce time to treatment, patients will be randomized using a deferral of consent procedure. The study protocol, deferred consent documents (patient and surrogate) and any subsequent modifications will be reviewed and approved by the local ethics committee responsible for oversight of the study. Approval from the committee must be obtained before starting the study and will be documented in a letter to the Sponsor (and any Participating Site Investigators).

The deferred consent process is described in Section 5.4 and will include an e-consent process or a paper-based consent process. Where permitted, for subjects who cannot provide consent themselves, a legally authorized representative, or person with power of attorney, may sign the consent form. A copy of the consent form will be given to the subject, the legally authorized representative, or the person with power of attorney; and this fact will be documented in the subject's clinical record. If new safety information results in significant changes in the risk/benefit assessment, the consent form should be reviewed and updated if necessary. All patients (including those already treated) will be informed of the new information.

#### 7.4 Monitoring

The AcT trial is a pragmatic registry embedded trial testing if intravenous tenecteplase (an intravenous thrombolytic drug tested and found safe in multiple phase 2 and one phase 3 trial is patients with acute ischemic stroke) can replace intravenous alteplase (the current standard care) in patients who are otherwise eligible to receive the latter in routine care. The emphasis in trial execution will therefore be on making sure that the "right" patient receives the appropriate intervention (i.e., correct randomization, treatment assignment) with adequate assessment of primary outcome (i.e., complete, correct, and timely blinded event ascertainment).

To align the requirements of good clinical practice with the considerations in a pragmatic randomized clinical trial, a risk-based approach to monitoring will be used. The registries will use their existing infrastructure and mandate to focus on quality patient care. Central monitoring will be the focus with limited on-site risk-based monitoring (if required) in co-ordination with the registry coordinators.

The following steps will be in place and monitored:

- 1. Randomization: The randomization module is built by the CRU at the University of Calgary and the electronic data capture vendor. The module and the mechanisms to maintain allocation concealment throughout the trail will be written down, signed by the sponsor and the electronic data capture vendor will be available for assessment. The randomization module will be tested at a frequency determined by the electronic data capture vendor current quality control practices to ensure that the above requirements are met.
- 2. Consent: Where approved by the local ethics review board, to reduce time to treatment, patients will be randomized using a deferral of consent procedure. Sites will receive a check list and automated emails from the sponsor reminding them to obtain consent. Upon request, the

electronic data capture vendor shall make available detailed consent information, including patient signatures to authorized study personnel. Sites will document in a checklist (see section 5.3 above) if consent has been obtained, from whom and reasons if consent could not be obtained. If consent could not be obtained in spite of best efforts (no surrogate or surrogate cannot be contacted), the patient will continue in the trial. Where approved by local ethics committees and if electronic consent was not possible, the last page of the signed paper consent form for each subject will be sent for central review.

With the exception of patients who died within 7 days or who are unable to provide consent and do not have any legal representatives, sites are expected to obtain consent within 7 days of subject enrolment or before discharge, whichever is earlier. In subjects who die, and consent has yet to be obtained, sites are expected to make reasonable efforts to obtain consent from legal representatives. A letter of bereavement may be provided to sites to send to the next of kin that provides information on the patient's enrolment. If subjects or, if incapacitated, their legal representatives, withdraw from further participation (including long-term follow-up by record linkage), sites will inform the sponsor about this within 7 days of this happening. Subjects may withdraw consent for further contact but continue follow-up via record linkage. In the event that consent is withdrawn, data collected up until the point of withdrawal will be used for analysis. The site will update the patient consent log and inform the sponsor of the same.

3. Conduct of the trial: This trial is a pragmatic randomized controlled trial embedded within registries (QuICR and OPTIMISE) that are focused on improving quality of health care delivery in patients receiving acute stroke treatments such as thrombolysis and EVT. The sponsor will therefore help support the efforts of the registries in educating and implementing best clinical practices in all participating sites.

Delegation Logs: The site qualified investigator (QI) will have primary responsibility for screening and enrolling patients within the trial. The site QI will, along with the sponsor, inform and train local qualified physicians and co-ordinators to screen, randomize and administer allocated drug. A delegation of authority log will document the personnel who have completed this training and can enrol patients into the trial. The delegation log will also document key trial-specific tasks that may be delegated to other members of the team, including site co-ordinators. Assessment of primary outcome is done centrally using phone call and is the sponsor's responsibility. The sponsor will keep a delegation log of personnel trained in this task.

Training Logs: Through sponsor-initiated study start up meetings, site QI initiated meetings or through emails/webinars, local qualified physicians treating acute stroke patients as per routine care and site co-ordinators will be informed and trained to screen, randomize and administer allocated drug (as described in the Delegation of Authority Log section above). A training log for these training sessions will be maintained. We will require all randomizing investigators and site co-ordinators to undertake an online training procedure for the trial. This training will be required prior to activation of an individual's randomizer access. We will log their successful training centrally and will provide sites with lists of trained personnel. In addition, the sponsor will periodically provide the sites with posters, checklists and other educational material to help

with the conduct of the trial. Finally, the sponsor will train personnel centrally for assessment of 90-120 day outcome. A training log for the above sessions will be maintained centrally.

Documentation to support qualification of individuals: The Qualified Investigator at the site, and the site lead research co-ordinator CV's and documentation supporting current training in GCP and Health Canada Division 5 will be collected.

Since physicians administering intravenous thrombolysis to patients with acute stroke are qualified to do so as part of routine standard of care, the site QI will ensure that physicians enrolling patients continue to remain qualified to screen and treat acute stroke patients annually. This will be done by ensuring that all physicians with randomizer access continue to be actively licenced to practice medicine in their jurisdiction (e.g. CPSO, CPSA) by collecting annual printouts from those regulatory bodies confirming their active license.

- 4. Interventions: The trial will capture if a) the correct drug b) the correct dose was administered c) and c) the vial LOT number and expiry date of the administered drug in the secure database maintained by the data management vendor. (see section 5.3).
- 5. Data linkages and flow: The data flow is designed to
  - a) Ensure patient confidentiality. The sponsor will not have access to the patient's Health Care Number that could reidentify individual patients.
  - b) Collate all data from multiple existing data sources to develop a final de-identified trial database that only has the unique Trial ID.

To fulfil the above objectives, the data flow shown in Figure below will be followed. The Trial database is developed by the Clinical Research Unit (CRU) at the University of Calgary and maintained by another data management vendor. ..

Each subject enrolled in the trial gets a unique Trial ID. The Trial ID is stored in the secure Trial Database. Each patient in the QuICR or OPTIMISE registries also has a registry identifier (herewith called Registry ID). The sites will enter the Registry ID in the secure Trial Database. An automated email from a secure server will go to the site reminding them to enter the Registry ID into the Trial Database. The sponsor will be able to check if the Registry ID is entered into the Trial Database but will not have "read access" to individual Registry IDs.

The designated Alberta Health Service analyst for QuICR (privacy assessed) and the site coordinators for OPTIMISE trial sites have access to the Registry ID and patient Health Care Numbers. Through their "read access" of the Trial ID and the Registry ID in the trial database, they will be able to then provide the Trial ID and the linked Health Care Numbers to the Canadian Institute for Health Information (CIHI).

CIHI and the QuICR and OPTIMISE registries will all then provide data labelled with the Trial ID only back to the sponsors. This final database with Trial ID as the only identifier will be the data available to the Investigators for analysis. Quality of the data linkages will be ascertained by qualified personnel with expertise in health service data linkages.

[figure not shown]

Figure showing data workflow within the AcT Trial.

# SAE, Serious Adverse Events; CIHI, Canadian Institute for Health Information; DAD, Discharge Abstract Database.

Version 2.0

35

- 6. Blinded Primary Outcome Assessment: A blinded assessor trained in administering the Rankin Focused Assessment method and DQ-5D-5L will perform the 90 to 120-day outcome assessments. The definition of a blinded assessor is that they are blinded to the treatment allocation and not involved in the patient's care. This person will sign a form that attests to the blinding as described above for performing all outcome assessments. Protocol deviations will be reported for any 90-120-day assessments that were performed by an "unblinded" assessor. Every effort will be made to collect an outcome assessment on each subject and have minimal "lost to follow-up assessments". Occasionally, the local site staff may be requested to contact the subject for this information...Cognitive assessment swill be completed directly by consenting participants using an online, automated assessment platform, with login via Trial ID only, so no bias is possible and identifiable data will not be captured.
- 7. Safety data: Details on mechanisms to be utilized in the trial to collect safety data and data on AEs is described in section 5.11. The sponsor will work the sites and the registries to ensure that all secondary and safety outcomes for the trial that are available through the registries (see Section 5.9) are entered within 90 days of subject enrolment.
- 8. Change in Study Personnel: When there are any changes to study personnel during the trial, it is the site's responsibility to notify the sponsor. Personnel who are no longer active at the site will be assigned an "inactive status" and their data privileges modified appropriately. The sponsor will maintain a log of any and all such changes. In co-ordination with the site co-ordinator, the sponsor will ensure access to all trial specific educational material to any new study personnel listed by the site.

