in the trial. Subjects or, if incapacitated, their legal representatives, will have the right to withdraw from further participation (including long-term follow-up by record linkage). Subjects may withdraw consent for further contact but continue follow-up via record linkage. In the event that consent is withdrawn, data collected up until the point of withdrawal will be used for analysis.

We will provide an option for a site-specific electronic consent application with electronic signature support that will be linked to the randomization tool. This solution shall be made available via a secure web-application. Alternatively, sites can print the consent form from the site and upload a scanned signed paper version. The deferred consent capture process shall consist of the following steps:

- 1) An electronic or paper physician script will be made available to the physician prior to enrolling a patient in the trial. This script will contain information that the physician can use as guideline to help inform the patient/shared decision maker (SDM) about the trial. The use of this physician script is not mandatory;
- 2) An electronic or paper information sheet will also be made available to the physician to help him/her inform the patient or shared decision maker (SDM) about the trial.
- 3) If and when the patient is capable of communicating and/or the SDM is available, the physician will provide them with the information in the sheet above. It is recognized that sharing of the information sheet with patient/SDM may happen before, during or after randomization;
- 4) After randomization has been completed for a patient, a unique identifier (study ID) will be assigned to each patient by the application, shown on-screen to the physician or site-coordinator and sent via e-mail to the site co-ordinator;
- 5) After treatment has been administered, as an added quality assurance step, a randomization validation process will be initiated. This process will confirm whether the drug and dosage used match the randomization values and, if the trial information sheet was shown to the patient and/or SDM;
- 6) Once the randomization process has been completed, in conjunction with the validation exercise, the site co-ordinator shall connect to the electronic consent capture application via a PC, tablet, or web-enabled mobile phone;

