#### 5.5 Proposed methods for protecting against sources of bias

The trial will have allocation concealment and blinded endpoint assessment. Given the time sensitive nature of acute stroke treatment, blinding the enrolling health personnel and patient to treatment allocation is not practical. Primary clinical outcome data (assessed using the modified Rankin Scale) will be determined by the Rankin Focused Assessment (RFA) method using centralized telephone interviews conducted by central trial personnel blinded to treatment allocation. The trial coordinator may contact the site to help schedule phone follow-ups. Follow-ups will be scheduled 90 to 120 days after randomization. The manual of procedures (MOP) will describe in detail the Rankin Focused Assessment method for use by central trial personnel.

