#### 5.9 Primary and secondary outcome measures

#### Primary Outcome: modified Rankin Scale 0-1 at 90 - 120 days

#### **Secondary Outcomes:**

- 1. Discharge destination (home, early supported discharge, rehabilitation facility, long term care, death) \* #
- 2. Home time (defined as number of days subject spends at home after index stroke event) 
- 3. Actual 90-120 day mRS score\*#
- 4. Door to needle time\*#
- 5. Door-in-door-out (DIDO) times at Primary Stroke Centres\*#
- 6. Recanalization status (mTICI score) at first angiographic acquisition in patients taken to the angio-suite for the purpose of administering EVT\*#
- 7. Proportion of patients administered EVT \*#
- 8. Door-to-groin puncture time in patients undergoing EVT\*#
- 9. CT-to-puncture time in patients undergoing EVT\*#
- 10. Return to baseline level of functioning
- 11. Cognition assessed via a brief, on-line cognitive assessment tool.

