#### 5.10 How will the outcomes be measured at follow up?

The primary outcome (assessed using the modified Rankin Scale) will be determined by the Rankin Focused Assessment (RFA) method using centralized telephone interview by trained study personnel blinded to treatment allocation. The Rankin Focused Assessment consists of a 4-page form, accompanied by a 5-page Instructions. Details will be provided in the MOP.

Secondary outcome measures described above are all available through the QuICR and OPTIMISE registries and will be collected from those data sources. The home time outcome will be determined through linkage with administrative data to calculate the total time in the first 90 days after index event that a stroke patient is not an inpatient. Processes for administrative linkages within Alberta, Ontario and potentially other participating sites will be different based on local resources and policies. Return to baseline level of functioning will be determined using the same centralized telephone interview used to determine the primary outcome. Cognition will be assessed using an on-line assessment platform, with a login by Trial ID (no personal ID provided to the cognitive platform) and the cognitive data output to the trial database by Trial ID. These strategies and methods will be detailed in a manual of operations.

Primary safety outcomes death and symptomatic ICH will be collected through the trial database

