#### 11. Missing data

Since the trial enrolls participants using a deferred consent approach, participants with missing mRS because of refusal of consent will be excluded completely from the analysis. Under the ITT principle, all remaining patients who are randomized are included in the analysis. Thus, every effort will be made to keep all missing data to a minimum i.e., < 5%. If, despite best efforts, there are missing data, then for the primary outcome analysis, data will be assumed to be missing completely at random (MCAR). Sensitivity analyses will be conducted to examine the impact of MCAR assumption on study conclusions using available case analysis and multiple imputation methods. Similarly, assumptions and missing data methods will be adopted for analysis of secondary outcomes.

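### Cognition is scored only in consenting patients who complete an online test themselves, so the result is selected by survival and ability; the protocol's statement that bias is impossible holds at most for assessor bias, and the SAP has no cognition analysis

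*Combined protocol and SAP*

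**What the plan says.** Protocol 5.9 lists, as secondary outcome 11, "Cognition assessed via a brief, on-line cognitive assessment tool". The synopsis list of outcomes omits it.

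Protocol 5.10 gives the mode: "Cognition will be assessed using an on-line assessment platform, with a login by Trial ID". It describes no telephone, assisted or proxy version and no score for a patient who has died or cannot do the test. It adds: "These strategies and methods will be detailed in a manual of operations". That manual is not among the documents.

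Protocol 7.4, item 6, on blinded outcome assessment, says that consenting participants complete the test directly, "with login via Trial ID only, so no bias is possible and identifiable data will not be captured".

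Two other provisions matter. Protocol 5.5 says that "blinding the enrolling health personnel and patient to treatment allocation is not practical". Protocol 5.4 expects some participants to be unable to act for themselves: "Subjects or, if incapacitated, their legal representatives, will have the right to withdraw from further participation". It also lets a patient stay in the trial without consent when no surrogate can be reached.

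On analysis, protocol 6.6 has a general rule that does not name cognition: "The continuous secondary outcomes will be analyzed using analysis of covariance (ANCOVA) and mixed-effects regression". The outcome table in SAP 9 has no cognition row. SAP 11 assumes that missing primary-outcome data are missing completely at random, with available-case and multiple-imputation sensitivity analyses. It then says: "Similarly, assumptions and missing data methods will be adopted for analysis of secondary outcomes".

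**The concern.** A score exists only for a patient who is alive, has consented, and can log in and finish the test. Severe aphasia, cognitive loss, marked disability and death all remove the score. Each is a consequence of the stroke that a thrombolytic can change. The arms compared are therefore not the arms randomised but the completers within each, and who completes depends on the outcome.

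An automated platform with an anonymous login answers a different question: whether an assessor who knows the allocation could influence the score. It does not address who has a score. Patients also take the test knowing which drug they received, so even apart from selection the statement is broader than the design supports.

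At stake is the interpretation of one secondary outcome. A null or favourable cognition result could be reported under a protocol statement that bias was ruled out, when the comparison leaves out those most affected.

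**Working it through.** The documents give no planning figure for cognition, so there is none to reproduce. They also give no completion rates and no SD for the test. Everything below is an illustration on assumed inputs. Only the 1:1 allocation and the total of 1600 (800 per arm) come from the plan (protocol 6.1).

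**1. What the written rules do with an unscored patient**

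- ANCOVA or a mixed model (6.6): the patient drops out, and the comparison is among completers.
- Missing completely at random (SAP 11): assumes that absence is unrelated to cognition. This is not credible for a cognitive test after stroke.
- Multiple imputation (SAP 11): under missing at random, it gives a dead patient a living patient's score, and gives a patient who could not do the test a score as if able. Neither outcome counts as bad.

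**2. Threshold model**

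Latent cognition is N(0,1) on alteplase, and a score is seen only above a threshold. A share q is unscored on alteplase and q + a on tenecteplase. Write c = z(q), c' = z(q + a) and d = c' − c. The alteplase completers' mean is φ(c)/(1 − q).

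Take q = 0.30 and a = 0.05: c = −0.524, c' = −0.385, d = 0.139, alteplase completers' mean 0.497.

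- *Pattern A, the drug lowers every score by d.* Tenecteplase completers' mean = −0.139 + φ(0.385)/0.65 = −0.139 + 0.570 = 0.431. Observed difference −0.066 SD against a true −0.139 SD: attenuation 1 − 0.066/0.139 = 53%. Power falls from 0.79 with everyone scored to 0.35 in completers.
- *Pattern B, the drug only makes the weakest patients untestable.* Tenecteplase completers' mean = 0.570. Observed difference 0.570 − 0.497 = +0.073 SD in favour of the drug that disables more patients (z = 1.75).

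Over q = 10-50% and a = 3-10 points, attenuation in A is 31-66% and the false benefit in B is +0.04 to +0.17 SD. At the mild end (10% against 15% unscored, pattern A), completers keep power of 0.97.

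**3. mRS-group model**

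Assumed shares for mRS 0-1 / 2-3 / 4-5 / dead: 35/30/22/13%. The first is the plan's alteplase rate; the rest are assumed. Assumed mean cognition: 0.5, −0.3 and −1.2 SD in the three surviving groups. Assumed completion: 50/30/5% (low) or 85/65/25% (high).

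Share scored, low: 0.35×0.50 + 0.30×0.30 + 0.22×0.05 = 0.276. High: 0.2975 + 0.195 + 0.055 = 0.548.

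Example, low completion, 5 points moved from mRS 2-3 to 4-5:

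- before: (0.0875 − 0.0270 − 0.0132)/0.276 = 0.171
- after: (0.0875 − 0.0225 − 0.0162)/0.2635 = 0.185
- difference: +0.014 SD

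| Shift on the worse drug | Completers, low / high | All survivors scored |
|---|---|---|
| 5 points, mRS 2-3 to 4-5 | +0.014 / −0.008 | −0.052 |
| 3 points, mRS 2-3 to death | +0.016 / +0.013 | +0.003 |
| 5 points, mRS 0-1 to 2-3 | −0.057 / −0.057 | −0.046 |
| 5 points, mRS 0-1 to 4-5 | −0.046 / −0.068 | −0.098 |

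With SE = 1.05 × √(1/n1 + 1/n2), the SE is 0.07-0.10 in completers and about 0.056 with all survivors scored. In the first row, selection removes or reverses the signal. That signal is within noise even with every survivor tested (−0.052/0.056 = −0.92). In the last two rows, completers still show −0.05 to −0.07 SD.

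**The case against.** **The sentence is about blinding.** It sits in the item on blinded assessment, and its reasoning (automation, Trial ID login) concerns assessor influence and identifiability. A reader might infer that the protocol claims completers represent all patients. No document says that. What stands is that the wording has no limit.

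**There is hardly a planned comparison.** One might say that the planned cognition comparison cannot see a drug that leaves more patients disabled. The documents do not support this. The SAP plans no specific cognition comparison, and the generic rule does not say that the score is continuous. The working also shows that completers can keep much or nearly all of the signal under some patterns. The supportable claim is attenuation, with reversal under some patterns.

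**The plan has more than a missing-completely-at-random assumption.** SAP 11 extends its imputation methods to secondary outcomes, and the unseen manual may describe help with the test or reasons for non-completion. Both points are fair. Imputation does not represent death or inability, however, and their handling in the analysis belongs in the SAP.

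**A ranked composite is not clearly better.** With ranks for dead, unable and score, 800 per arm and an assumed within-group SD of 0.8, simulated power in the mRS-group model was about 6-16% for the 5-point shift from mRS 2-3 to 4-5, and 18-22% for the 3-point shift to death. It also overlaps with mRS and mortality. This stands as a reason not to make it the only permitted analysis. Its merit is that it keeps every randomised patient and counts death and inability as bad outcomes.

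**The consequence is limited.** mRS 0-1, mRS 0-2, ordinal mRS and mortality are compared directly, so extra disability or death is assessed there.

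**Conclusion.** The point holds in a limited form. The cognition result is selected by survival and by ability to do the test. The statement in protocol 7.4 is true at most of assessor bias. The SAP has no cognition row, and the general rules that remain do not represent death or stroke-related inability.

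A between-arm difference could be attenuated (31-66% in the threshold model when all scores shift) and, under some patterns, reversed (+0.04 to +0.17 SD when the drug mainly makes the weakest untestable). These sizes rest on assumed shares unscored, an assumed normal latent score and assumed shifts. The documents give none of these, so the ranges are not forecasts.

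A reader might go further and infer that harm would always be hidden, or that the non-inferiority finding is weakened. Neither follows: some patterns remain visible among completers, and the primary conclusion does not use cognition. The change is worth making before analysis, in proportion to a secondary outcome.

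**What to change.** 1. In protocol 7.4, item 6, limit the statement to assessor bias.
2. Add a cognition row to SAP 9 naming the score, the model and the handling of death and inability.
3. Have the blinded caller at 90-120 days record whether the test was done and, if not, whether the stroke was the reason.
4. Report completion and reasons for non-completion by arm, and label the completers-only comparison descriptive.
5. Add, at least as a sensitivity analysis, a comparison in all intention-to-treat patients that ranks death lowest, then stroke-related inability, then the test score. Impute non-stroke missingness (for example no internet access, or refusal of the test) using the mRS from the same call. Report the composite with its components.

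Cost: SAP and protocol wording, and one short item on a call already scheduled. The drawback is that the composite partly overlaps with mRS and mortality, so it must be read beside its components and not as a pure measure of cognition.
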